4.2 Rationale

4.2.1 Rationale for the Trial and Selected Subject Population

Details regarding specific benefits and risks for subjects participating in this clinical trial may be found in the accompanying Investigators Brochure (IB) and Informed Consent documents.

Subjects in clinical trials generally cannot expect to receive direct benefit from treatment/vaccination during participation, as clinical trials are designed to provide information about the safety and effectiveness of an investigational medicine.

Protocol/Amendment No.: 004-02

The current protocol is expected to extend the experience with MK-8521, observe safety parameters and to assess the effect of multiple daily doses of MK-8521 on change from baseline in A1C and body weight after 12 weeks in subjects with T2DM. In particular, the current trial will allow for a direct comparison of the effects of MK-8521 and liraglutide on safety, tolerability as well as efficacy measured as changes in A1C and body weight.

Approximately 160 subjects with T2DM will receive MK-8521 300 μg QD, MK-8521 180 μg QD, placebo QD or open-label liraglutide QD for 12 weeks. Safety data and the effect of MK-8521 on A1C and body weight will be assessed at 12 weeks. The rationale for this approach is to examine the safety, and efficacy of MK-8521 in a larger cohort of subjects with baseline characteristics that resemble the target population for this compound, in an outpatient setting. The rationale for the duration of the study is to allow for sufficient time for glycemic efficacy to reflect changes in A1C and for significant changes in body weight to occur.

Randomization of subjects will be stratified based on baseline A1C, BMI and AHA washout status as these factors may affect the magnitude of response to therapy. Any imbalance of these characteristics between treatment arms may confound the actual treatment effect.

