8.1.1 Efficacy Analysis

The primary and key secondary efficacy endpoints, primary analysis population, and statistical methods that will be employed for the efficacy analyses are presented in Table 11 below.

Product: MK-8521

Protocol/Amendment No.: 004-02

Table 11 Summary of Analysis Strategy for Key Efficacy Endpoints

Endpoint	Statistical Method	Analysis Population	Missing Data Approach
Primary efficacy endpoint: A1C – Change from baseline at Week 12	cLDA	FAS	Model-based
Body Weight – Change from baseline at Week 12	cLDA	FAS	Model-based
Fasting Plasma Glucose – Change from baseline at Week 12	cLDA	FAS	Model-based

For the primary efficacy analyses, a constrained longitudinal data analysis (cLDA) method proposed by Liang and Zeger [22] will be used. The cLDA model will include terms for treatment (4 arms), time, stratification factors of A1C (<8.5%, $\ge8.5\%$), BMI (<30 kg/m2, ≥30 kg/m2) and AHA washout status (Yes, No), and the interaction of time by treatment, with the restriction of a common baseline mean across treatment groups. An unstructured covariance matrix will be used to model the correlation among repeated measurements.

The primary comparisons for efficacy endpoints are each of the MK-8521 doses versus placebo. The primary population for all efficacy analyses will be the Full Analysis Set (FAS), comprised of all subjects who received at least one dose of trial therapy and have a baseline measurement or a post-randomization measurement.

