8.2.5.1 Efficacy Analyses

To address the primary objective, the analysis of change from baseline in A1C at Week 12 will be performed using a constrained longitudinal data analysis (cLDA) method proposed by Liang and Zeger. This repeated measures model assumes a common mean across treatment groups at baseline and a different mean for each treatment at each of the post-baseline time points. The response vector consists of baseline and the values observed at each postbaseline time point. The cLDA model will include terms for treatment, time, stratification factors of A1C (<8.5%, $\ge8.5\%$), BMI ($<30 \text{ kg/m}^2$, $\ge30 \text{ kg/m}^2$) and AHA washout status (Yes, No), and the interaction of time by treatment. Time is treated as a categorical variable so that no restriction is imposed on the trajectory of the mean over time. An unstructured covariance matrix will be used to model the correlation among repeated measurements and hence avoids the potential bias that could result from the use of specific structured covariance models. If the unstructured covariance model fails to converge with the default Newton-Raphson algorithm, the Fisher scoring algorithm or other appropriate methods can be used to provide initial values of the covariance parameters. In the rare event that none of the above methods yield convergence, a structured covariance such as Toeplitz can be used to model the correlation among repeated measurements. In this case, the empirical option will be used because the sandwich variance estimator is asymptotically unbiased while the model-based variance estimator can substantially overestimate or underestimate the true variance. The Kenward-Roger adjustment will be used with restricted (or residual) maximum likelihood (REML) to make proper statistical inference. The cLDA model uses the maximum likelihood principle to estimate the parameters and account for missing data in an implicit fashion.

The primary hypothesis will be assessed by an ordered testing procedure, comparing each of the two MK-8521 doses to placebo at Week 12, using the above cLDA model. This testing procedure first tests the 300 μg dose. If a statistically significant result (i.e., p<0.05) is observed on the 300 μg dose, the primary hypothesis (for A1C) is considered met and then the 180 μg dose is tested. The secondary hypotheses (for body weight and FPG) will be assessed only if the primary hypothesis is met, regardless of the outcome of the 180 μg vs placebo comparison.

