Power and sample size will be re-assessed based only on the conditional standard deviation at the interim analysis and will be performed by the unblinded statistician. If any sites are identified as having low compliance as defined in Section 8.2.4, the goal of the sample size adjustment will be to ensure adequate power in the mFAS population. The conditional standard deviation for A1C and body weight will be estimated from the cLDA model in the mFAS population. Implementation details will be provided in the siDMC charter.

As stated in Section 8.2.7, the initial sample size (40 per arm) will provide 85% power for the A1C hypothesis and 87% power for the body weight hypothesis, resulting in 74% overall power for success in testing both hypotheses. The sample size will be increased, if necessary, so that there is at least 80% power for each individual hypothesis for A1C and body weight, and at least 74% overall power for both hypotheses in the mFAS population. A conservative estimate of SD will be used to calculate the power and sample size. The following rules will be used for adjusting the sample size:

- For A1C, 0.1% will be added to the point estimate of conditional SD from the interim data. For example, if the point estimate is 1.1%, 1.2% will be used in the sample size computation;
- For body weight, 0.2 kg will be added to the point estimate of conditional SD from the interim data. For example, if the point estimate is 2.7 kg, 2.9 kg will be used in the sample size computation.

Protocol/Amendment No.: 004-02

If necessary, the sample size will be increased to the minimum sample size that meets the power criteria above, subject to a maximum of 45 subjects per arm in the mFAS population and a total maximum of 200 subjects randomized. If the power criteria above cannot be met within these sample size constraints, the trial will continue using the maximum permissible sample size under these constraints.

Table 14 Summary of Planned Efficacy and Safety Interim Analysis Strategy

Key Endpoints for Interim Analysis	Timing of Interim Analysis	Purpose of Interim Analysis	
Change in body weight at week 12	When at least 50% of randomized subjects either	 Program planning Sample size re-	
C1 : IID : W 1 12		estimation, • Study termination for futility.	

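### The primary cLDA carries the three stratification factors only as time-constant effects, so it cannot let change from baseline differ by stratum; the cost is modest and time-by-stratum terms remove it cheaply

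*Combined protocol and SAP*

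**What the plan says.** Section 8.2.5.1 sets up the primary analysis of A1C as a constrained longitudinal model. "The response vector consists of baseline and the values observed at each postbaseline time point". "This repeated measures model assumes a common mean across treatment groups at baseline", with separate means by arm afterwards. "An unstructured covariance matrix will be used to model the correlation among repeated measurements". On the mean structure, "The cLDA model will include terms for treatment, time, stratification factors of A1C" and BMI, and the list closes with "AHA washout status (Yes, No), and the interaction of time by treatment", the single interaction named. Section 8.1.1 gives the same list: "The cLDA model will include terms for treatment (4 arms), time, stratification factors of A1C" and so on. Neither section has a time-by-stratum term.

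Section 4.2.1 says that randomization is "stratified based on baseline A1C, BMI and AHA washout status as these factors may affect the magnitude of response to therapy". The supportive per-protocol ANCOVA in Section 8.2.5.1 enters the strata and the baseline value as covariates of the Week 12 outcome. For sample-size re-estimation, Section 8.2.9.2 states: "The conditional standard deviation for A1C and body weight will be estimated from the cLDA model in the mFAS population".

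**The concern.** When baseline is one of the responses, a stratum coefficient that is the same at every visit describes a gap present at baseline and carried unchanged to Week 12. It says nothing about change. The primary model therefore assumes equal mean change in the two A1C strata, the two BMI strata, and in washed-out and other subjects, within arm. That sits badly with the stated reason for stratifying, and it differs from the ANCOVA.

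Two of the three factors make the assumption doubtful:

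- **A1C stratum.** It is a cut of a screening or Visit 2 value (Section 5.4), so its gap would be expected to shrink with regression to the mean. The model holds it constant.
- **Washout.** Washed-out subjects reach baseline after at least 8 weeks off the second agent plus a 2-week run-in. Section 4.2.3.1 says A1C reflects the past 3 to 4 months, so their A1C could still be rising at Day 1. The documents do not say by how much.

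At stake are some precision, robustness to one kind of dropout, and the conditional SD used to resize the trial.

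**Working it through.** **Inputs from the documents.** 40 per arm, 1:1:1:1; conditional SD 1.1%; difference 0.8%; two-sided alpha 0.05; attrition 8% by Week 6 and 16% by Week 12; conditional correlation 0.76732; effective n 35; half-width 0.52% (all Section 8.2.7). A1C is measured at Day 1 and Weeks 6, 9 and 12 (Section 6.0).

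**1. The plan's own figure.** With 40 × 0.92 = 36.8 subjects at Week 6 and 40 × 0.84 = 33.6 at Week 12, and ρ² = 0.5888:

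effective n = 1 / [(1 − 0.5888)/33.6 + 0.5888/36.8] = 35.4.

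At n = 35, SE = 1.1 × √(2/35) = 0.263. Power is 86.0% by the normal approximation and 85.1% by noncentral t; the half-width is 0.515 or 0.525. The stated 85% and 0.52% reproduce.

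**2. Why the strata cancel.** Let s be a stratum indicator and γ its coefficient. The planned mean is E[Y(t)] = μ(t) + τ(arm, t) + γs, with τ = 0 at baseline. Then

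E[Y(12) − Y(0)] = μ(12) − μ(0) + τ(arm, 12),

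which is free of γ. Conditioning on baseline with slope b leaves a stratum coefficient of γ(1 − b) at Week 12. The strata therefore still enter the estimator, but in a form tied to the baseline gap.

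**3. Closed-form size.** Let d be the shift in Week 12 A1C between strata, given baseline, for one factor with share p = 0.5. Modelling it lowers the SD from 1.1 to √(1.21 − d²p(1 − p)).

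| d (assumed) | SD after | SE falls by | Power, n = 35 (from 86.0%) |
|---|---|---|---|
| 0.2 | √1.2000 = 1.095 | 0.4% | 86.3% |
| 0.3 | √1.1875 = 1.090 | 0.9% | 86.7% |
| 0.5 | √1.1475 = 1.071 | 2.6% | 87.8% |

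**4. Simulation of both cLDA models.** 160 subjects, stratified blocks, REML-type fit, unstructured covariance, 1,000 runs per setting, model-based SEs without Kenward-Roger. Assumed: slope on baseline 0.6; stratum shares about 0.5, 0.6 and 0.4; adjacent-visit correlation 0.85.

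| d for A1C / BMI / washout (assumed) | SE as planned | SE with time-by-stratum | Ratio |
|---|---|---|---|
| none | 0.264 | 0.260 | 1.015 |
| 0.2 / 0.2 / 0.3 | 0.259 | 0.256 | 1.015 |
| 0.5 / 0.5 / 0.5 | 0.252 | 0.240 | 1.050 |

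In the last row power is 89.9% as planned and 91.2% with the added terms. The actual spread of the estimates hardly moves (0.246 against 0.245). Stratified randomization already delivers most of the precision, and the planned SE fails to recognize it. With no stratum effect on change, the planned model's SE (0.264) is slightly larger than with the strata left out (0.259).

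Two further simulations assumed a washout effect only. One found an SE excess of about 1% with no shift and 3% to 6% for shifts of 0.5 to 0.8. The other (35% washout, 1,200 runs) gave variance ratios of 1.04, 1.08 and 1.17 for shifts of 0, 0.5 and 0.8; the square roots are 1.02, 1.04 and 1.08. Its power was 85.0% against 85.6%, 85.5% against 87.6%, and 86.2% against 90.2%, planned model first. A shift of 0.8 is the far end of the assumed range.

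**5. Dropout** (true difference −0.8).

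| Dropout pattern | Bias as planned | Bias with time-by-stratum |
|---|---|---|
| Uneven by stratum, alike across arms, d = 0.5 for all | −0.007 (Monte Carlo SE 0.008); +0.002 with 8,000 subjects | −0.007; +0.001 |
| Crossed, d = 0.2 / 0.2 / 0.3 | −0.024 | 0.000 |
| Crossed, d = 0.5 for all | −0.045 | −0.005 |

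Crossed means losses of 4% and 24% in placebo and 31% and 6% in the other arms, for washed-out and other subjects. This pattern exaggerates the effect. The reverse pattern (41% of washed-out placebo subjects lost, 12% elsewhere) shrinks it to −0.77 or −0.75 for washout shifts of 0.5 or 0.8, and the added terms restore −0.80. The sign depends on who leaves.

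**6. Re-estimation.** Taking the SE excess as a guide to the SD excess, 1% to 6% of 1.1 is 0.01 to 0.07. Section 8.2.9.2 already adds 0.1 deliberately.

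**The case against.** The strongest reply is that the plan delivers what it promises. The half-width of 0.52 implies an SE of 0.52/1.96 = 0.265, and the planned model returned SEs of 0.252 to 0.264 when dropout did not depend on stratum. What is forgone is extra power, and that depends on stratum effects for which the documents give no value. This stands.

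A reader might infer that the primary analysis ignores the stratification factors. It does not. Continuous baseline A1C, the variable behind the A1C stratum, is adjusted for through the response vector and unstructured covariance, and the strata keep the coefficient γ(1 − b) given baseline.

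A reader might also infer that any uneven dropout by stratum biases the comparison. Step 5 shows otherwise when the arms are alike. The crossed patterns are assumed; the plan expects 16% attrition overall. A crossed pattern is still conceivable: Section 5.9 discontinues subjects on FPG limits that tighten after Week 6, Section 5.6 specifies no rescue, and Section 5.9.1 leaves discontinued subjects without the scheduled procedures after their discontinuation and 14-day visits.

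The PP ANCOVA and the stratum-specific estimates in Section 8.2.8 cover part of the ground. Section 4.2.1 may also have effect modification in mind, which time-by-stratum terms alone would not model. But neither of those analyses supplies the missing terms for the primary one. On re-estimation, the likely SD excess is smaller than the deliberate pad, so it is a side effect of little weight.

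**Conclusion.** The concern holds as a modest point of efficiency and robustness. As written, the primary cLDA does not allow change from baseline to differ by A1C, BMI or washout stratum, although the trial stratifies because such differences are plausible. Its SE is about 1% to 1.5% too wide with nil to moderate stratum effects and about 3% to 6% with large ones; one set of runs reached 8% at the 0.8 extreme. The error is on the conservative side. A bias of about 0.02 to 0.05 A1C points on a true 0.8, or 3% to 6% of the effect, needs dropout that differs by arm and stratum together as well as a stratum effect on change.

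It would be tempting to call the primary test invalid or the trial underpowered. The documents support neither: 85% power reproduces, and the simulated planned model kept its coverage near 95% at 160 subjects. The sizes rest on assumed stratum effects, stratum shares, a baseline slope of 0.6 and assumed dropout patterns. The cancellation in step 2 rests only on the model as written.

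**What to change.** In Sections 8.1.1 and 8.2.5.1, add time-by-A1C-stratum, time-by-BMI-stratum and time-by-washout interactions to the cLDA. Use the same model for FPG, body weight, the mFAS analysis, the interim analysis and the conditional SD in Section 8.2.9.2. This also brings the primary model closer to the PP ANCOVA.

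The cost is a change of wording and a few parameters: 3 factors × 3 post-baseline A1C visits = 9, with a small loss of degrees of freedom among about 160 subjects. No simulation showed a larger SE with the added terms than under the planned model, even with no stratum effect on change. Section 8.2.1 allows for amending methods before any unblinding, so the change should be made before the interim analysis.

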3.0 OBJECTIVE(S) & HYPOTHESIS(ES)

3.1 Primary Objective(s) & Hypothesis(es)

In subjects with T2DM with inadequate glycemic control on metformin monotherapy, after 12 weeks of once-daily administration:

1. Objective: To assess the A1C-lowering efficacy of the addition of MK-8521 relative to placebo.

Hypothesis: 300μg/day or both doses of MK-8521 provide greater reduction in A1C relative to placebo.

2. Objective: To evaluate safety and tolerability of MK-8521.

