3.2 Secondary Objective(s) & Hypothesis(es)

In subjects with T2DM with inadequate glycemic control on metformin monotherapy, after 12 weeks of once-daily administration of MK-8521, to assess the effect relative to placebo on:

1. Body weight

Hypothesis: 300μg/day or both doses of MK-8521 reduce body weight relative to placebo.

2. Fasting plasma glucose

Hypothesis: 300μg/day or both doses of MK-8521 provide greater reduction in FPG relative to placebo.

- **3.** Fasting lipids (including LDL-cholesterol level, HDL-cholesterol level, triglyceride level).
- 4. Systolic and diastolic blood pressure

In subjects with T2DM with inadequate glycemic control on metformin monotherapy, after 12 weeks of once-daily administration of MK-8521, to estimate the effect relative to liraglutide on:

- **5.** Glycemic measures (A1C and FPG)
- **6.** Body weight
- 7. Fasting lipids (including LDL-cholesterol level, HDL-cholesterol level, triglyceride level).
- **8.** Systolic and diastolic blood pressure

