8.2.5 Statistical Methods

Statistical testing and inference methods for efficacy and safety analyses are described in Section 8.2.5.1 and Section 8.2.5.2, respectively. Efficacy results that will be considered to be statistically significant after consideration of the strategy for controlling the Type I error are described in Section 8.2.6 - Multiplicity. Nominal p-values may be computed for other efficacy analyses as a measure of strength of association between the endpoint and the treatment effect rather than formal tests of hypotheses. All statistical tests will be conducted at the 2-sided 0.05 significance level.

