
Protocol/Amendment No.: 004-02

In the event that fewer than 75% of the subjects in the 300 μ g dose group receive the full target dose, suggestive of dose-intolerance, the hypothesis test MK-8521 180 μ g vs. placebo will be performed first. In this case if the 180 μ g dose vs. placebo is statistically significant, the primary hypothesis (for A1C) will be considered met and then the 300 μ g dose will be tested.

If success is achieved in the test of the primary hypothesis (i.e., at least one dose of MK-8521 provides significantly greater reduction in A1C relative to placebo following the testing procedure described above), then each of the MK-8521 doses will be compared to liraglutide using the same ordered testing procedure above. Continuous efficacy endpoints such as FPG, body weight, LDL-cholesterol level, HDL-cholesterol level, triglyceride level, systolic blood pressure (SBP), and diastolic blood pressure (DBP) will be analyzed using the above cLDA method described for A1C. Change and percent change from baseline in triglycerides will be analyzed using multiple imputation (MI) of missing values (if any) in conjunction with a robust regression (RREG) approach that uses M-estimation. Because the percent change in triglycerides typically has a skewed distribution, the cLDA model which is based on the symmetric normal distribution is not appropriate.

The primary (A1C) and key secondary endpoints (FPG and body weight) will also be analyzed in the PP population using an ANCOVA model. The ANCOVA model will include treatment, stratification factors of A1C (<8.5%, $\ge8.5\%$), BMI (<30 kg/m², ≥30 kg/m²) and AHA washout status (Yes, No), and baseline value. By definition, there will be no missing outcome data in the PP population.

Key efficacy endpoints will also be analyzed in the mFAS population using the same statistical methods stated for the FAS population.

Table 12 summarizes the analysis strategy for all efficacy endpoints. The strategy to address multiplicity issues with regard to multiple treatment comparisons and multiple endpoints is described in Section 8.2.6, Multiplicity.

Table 12 Analysis Strategy for Efficacy Endpoints

Endpoint (All at Week 12)	Approach	Statistical Method	Analysis Population	Missing Data Approach
Primary				
Change from baseline in A1C	P	cLDA	FAS	Model-based
Change from basefine in ATC	S	ANCOVA	PP	NA
	S	cLDA	mFAS	Model-based
Key Secondary				
Change from baseline in FPG	P	cLDA	FAS	Model-based
	S	ANCOVA	PP	NA

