8.2.6 Multiplicity

The Type-I error rate over the multiple treatment comparisons (i.e., two MK-8521 doses versus placebo) for the primary hypothesis will be controlled by an ordered testing procedure. This testing procedure will first test the 300 μ g dose. If a statistically significant result is observed, then the 180 μ g dose will be tested and the primary hypothesis test will be considered successful, regardless of the outcome of the 180 μ g vs. placebo.

In the event that fewer than 75% of the subjects in the 300 μ g dose group receive the full target dose, the first test of MK-8521 vs. placebo will be performed at the 180 μ g dose. If the 180 μ g dose vs. placebo is statistically significant, then the primary hypothesis will be considered successful.

The secondary hypotheses for body weight and FPG are deemed supportive and will only be tested if significance is achieved at the corresponding dose level for A1C.

Comparisons involving other efficacy endpoints and other treatment comparisons (MK-8521 doses vs. liraglutide) are considered supportive or exploratory and will be made at α =0.05

Protocol/Amendment No.: 004-02

nominal level (two-sided) and 95% CIs will be provided. No multiplicity adjustment will be performed for these other comparisons.

From a safety standpoint, application of a multiplicity adjustment could potentially mask a safety concern. No multiplicity adjustment is planned for safety endpoints.

An interim analysis will be performed to assist in program planning, support sample size reestimation, and support assessment of whether the study should be terminated based on an assessment of the overall data and in consideration of programmatic goals (described in Section 8.2.9). This is not a pivotal trial and the trial will not be stopped early for positive results. Therefore, no alpha adjustment will be made for this interim analysis.

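### Sections 8.2.5.1 and 8.2.6 give different testing rules for 180 µg weight/FPG and for liraglutide, and the primary hypothesis in 3.1 omits a 180 µg-only win that the plan can call success

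*Combined protocol and SAP*

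**What the plan says.** **Weight and FPG.** After describing the A1C test of 300 µg and then 180 µg, section 8.2.5.1 says the secondary hypotheses "will be assessed only if the primary hypothesis is met, regardless of the outcome of the 180" µg versus placebo result. Section 8.2.6 says the same hypotheses "will only be tested if significance is achieved at the corresponding dose level for A1C".

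**Which section governs.** Section 8.2.5 says the efficacy results to be considered significant under the "strategy for controlling the Type I error are described in Section 8.2.6". Section 8.2.5.1 adds that the strategy for "multiplicity issues with regard to multiple treatment comparisons and multiple endpoints is described in Section 8.2.6". Neither section says which wins if they differ.

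**Liraglutide.** Under 8.2.5.1, once the primary hypothesis succeeds, "each of the MK-8521 doses will be compared to liraglutide using the same ordered testing procedure above". Section 8.2.6 treats these comparisons as supportive or exploratory at a nominal two-sided 0.05 and adds: "No multiplicity adjustment will be performed for these other comparisons". Section 3.2 sets no liraglutide hypothesis, only an aim "to estimate the effect relative to liraglutide on" the listed endpoints.

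**Primary hypothesis.** Section 3.1 states that 300 µg/day "or both doses of MK-8521 provide greater reduction in A1C relative to placebo". If fewer than 75% of the 300 µg arm receive the full target dose, 8.2.5.1 and 8.2.6 both test 180 µg first and treat significance there as success. Section 8.2.5.1 then tests 300 µg; 8.2.6 does not mention that test.

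**The concern.** Weight and FPG are the key secondary endpoints (8.2.3.1), and weight is one of the two hypotheses whose joint power drives the sample-size re-estimation in 8.2.9.2. Two analysts following different sections could report different 180 µg conclusions from the same data. The looser gate also protects less against a false 180 µg claim.

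The liraglutide comparisons are gated and ordered in one section and ungated and unadjusted in the other, so it is unclear whether a 180 µg result may be cited when 300 µg misses.

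In the switched order, a report could declare the primary hypothesis met on an outcome that the hypothesis as written does not contain. Under 8.2.6 alone, the 300 µg A1C result that should gate 300 µg weight and FPG is not provided for.

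Section 8.2.1 rules out a separate SAP, so no later document is planned in which to settle these rules.

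**Working it through.** **Inputs (8.2.7).** Two-sided alpha 0.05; 40 per arm, effective n 35 at Week 12. Differences and conditional SDs: A1C 0.8% and 1.1%; weight 2 kg and 2.7 kg; FPG 30 mg/dL and 40 mg/dL. The shared placebo arm gives a correlation of 0.5 between the two dose comparisons. The documents give no correlation between endpoints, so 0, 0.3 and 0.6 are assumed.

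**Reproducing the stated power.** SE = SD × √(2/35) = SD × 0.2390; power ≈ Φ(difference/SE − 1.960).

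| Endpoint | SE | Difference/SE | Power, normal | Power, t (68 df) | Plan |
|---|---|---|---|---|---|
| A1C | 0.263 | 3.04 | 86.0% | 85.1% | 85% |
| Weight | 0.645 | 3.10 | 87.3% | 86.3% | 87% |
| FPG | 9.56 | 3.14 | 88.1% | 87.1% | 88% |

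The stated powers reproduce. The 74% joint power in 8.2.9.2 is 0.85 × 0.87 = 0.74, which assumes independence.

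**How often the gates disagree.** They differ exactly when 300 µg is significant on A1C and 180 µg is not: P = P(300 significant) − P(both significant). The 300 µg effect is held at 0.8%.

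| 180 µg A1C effect | Bivariate normal | Simulation (400,000 trials, pooled t, 136 df) |
|---|---|---|
| 0.8% (design) | 0.8605 − 0.7730 = 0.0875 | 0.089 |
| 0.7% (assumed) | 0.8605 − 0.6946 = 0.166 | 0.168 |
| 0.6% (assumed) | 0.8605 − 0.5846 = 0.276 | 0.278 |
| 0.5% (assumed) | 0.8605 − 0.4531 = 0.407 | 0.409 |

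At the design effects, the gates disagree and 180 µg is also significant on weight or FPG in 8.8%, 8.3% and 7.1% of trials for endpoint correlations 0, 0.3 and 0.6. In those trials the reported result changes.

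**False 180 µg findings.** 300 µg has its design effects and 180 µg has none on any endpoint. The looser gate is read as opening both doses after a 300 µg A1C win.

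| False 180 µg result | Looser 8.2.5.1 gate | 8.2.6 gate |
|---|---|---|
| Weight or FPG, two-sided | 7.1–8.3% | 0.4–1.4% |
| Weight or FPG, beneficial direction only | 4.2–4.4% | 0.1% to about 1% |
| Weight alone, two-sided | 4.0–4.3% | 0.2–0.9% |

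If 8.2.5.1 is taken to imply the 300-then-180 order within each endpoint as well, its figures fall to 6.1–6.4% for either endpoint and 3.2–3.4% for weight alone.

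**Liraglutide.** With two null comparisons on one endpoint, the chance of any false positive is 9.1% if both are nominal (8.2.6) and 5.0% if they are ordered (8.2.5.1).

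**Primary hypothesis.** In the default order 180 µg cannot win alone, and 3.1, 8.2.5.1 and 8.2.6 agree. In the switched order, with a 180 µg effect of 0.8%, a 180 µg-only win has probability about 9% if 300 µg keeps its full effect, 54% at half the effect and 82% at none. The A1C error rate stays near 5% (4.95–5.04%) in each branch taken as fixed.

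**The case against.** The strongest defence is that the sections can be read together. In 8.2.5.1, *only if* sets a necessary condition for the secondary family, and the clause about 180 µg may mean no more than that a 300 µg win suffices for the primary, as 8.2.6 also says. Section 8.2.6 then adds the dose-level condition, and 8.2.5 and 8.2.5.1 both refer the reader there for multiplicity. This stands: the stricter gate satisfies both sections. But it has to be inferred, and the clause in 8.2.5.1 points the other way.

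On liraglutide, ordered testing also runs each test at 0.05, so the alpha level does not conflict. The gate and the order still do.

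On the switched order, the two statistical sections agree that 180 µg alone counts, and 8.2.5.1 does state the 300 µg follow-on test. An analyst would know what to do; the fault is that 3.1 was not brought into line and 8.2.6 is silent on the second step.

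On size, the larger false-positive figures are two-sided and pool weight with FPG, which neither section adjusts for. For weight alone the looser gate stays below 5%. The scenario of an inactive 180 µg dose also runs against the plan's premise: 4.1.2.2 reports near-maximal glycemic effects from 120 µg/day, and 4.2.2 expects notable A1C change at 180 µg. Estimates and confidence intervals are the same under either gate; only the formal claim changes. Section 8.2.6 calls the secondary hypotheses supportive and the trial not pivotal. These points keep the concern at moderate weight but do not reconcile the text.

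**Conclusion.** The concern holds on all three parts. The weight/FPG gate is worded two ways, the liraglutide comparisons have two statuses, and, only in the branch where fewer than 75% reach the full 300 µg dose, the success rule goes beyond the hypothesis in 3.1.

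At the design effects the gates disagree in about 9% of trials, rising to 17%, 28% or 41% if the 180 µg A1C effect is 0.7%, 0.6% or 0.5%. Those smaller effects are assumptions; the plan expects at least 0.8%. The false-positive contrast assumes that only 300 µg works, and its range reflects the assumed endpoint correlations.

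The primary A1C test is not inflated. The rules should be fixed, but the conflict does not threaten the main result.

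**What to change.** 1. State in 8.2.6 that it prevails over 8.2.5.1 on which tests are performed and which results may be claimed.
2. Amend 8.2.5.1 so that each dose's weight and FPG tests open only if that dose is significant on A1C, and delete the clause about the 180 µg outcome.
3. In 8.2.5.1, describe the liraglutide comparisons as nominal and supportive with 95% CIs, matching 8.2.6 and the estimation aim in 3.2.
4. Add to 8.2.6 the follow-on 300 µg A1C test in the switched order, as 8.2.5.1 already has it.
5. Reword the hypotheses in 3.1 and 3.2 to at least one dose, tested in the order given in 8.2.6.

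The cost is wording in four sections, with no added subjects, visits or procedures. Because it touches the primary and key secondary hypotheses, 8.2.1 requires a protocol amendment before any unblinding, so it should be completed before the interim analysis. If the rolling PK unblinding described in 8.2.5.1 has begun, the amendment should record that those with access took no part in it.

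The statistical price is that 180 µg weight and FPG cannot be claimed when 180 µg fails on A1C. At the design effects this gives up such a claim in about 7–9% of trials compared with the looser reading.
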